2.1.4 Evaluation of 18F-FAPI PET/CT in Predicting Lung Cancer Prognosis

Based on TNM staging and PERCIST criteria, this study evaluates the post-treatment reassessment, efficacy prediction, and prognostic assessment (AUC comparison of PFS/OS) of 18F-FAPI PET/CT in lung cancer. The research will analyze the monitoring capability of 18F-FAPI PET/CT in assessing tumor response post-treatment

and its value in prognostic evaluation, aiming to provide clinicians with a more precise tool for assessing treatment efficacy. It tracks the time from diagnosis to specific events (e.g., CR, PR, SD, PD, recurrence, death) in lung cancer patients to identify influencing factors. Survival rates over time are plotted using Kaplan-Meier curves to visually compare survival differences across groups. Additionally, Cox proportional hazards model multivariate regression quantifies the contribution of factors such as age and pathological stage to survival risk, aiding clinical decision-making.

3 Mechanism of Action and Research Scope of 18F-FAPI PET/CT

18F (97% β^+ , $T_{1/2}=109.7$ minutes) is currently the most widely used radionuclide in PET/CT due to its chemical, physical, and nuclear properties, making it an ideal choice for peptide-based imaging. 18F-FDG is the most commonly used PET tracer in oncology, serving as the preferred modality for tumor diagnosis and therapeutic efficacy evaluation. However, 18F-FDG PET/CT exhibits relatively low sensitivity and specificity for tumors with low invasiveness, high differentiation, or mucinous tissue, while physiological uptake in organs such as the oropharynx and digestive tract often obscures tumor metabolism and uptake. Additionally, mediastinal and hilar lymph nodes still show a high rate of false positives on 18F-FDG PET, whereas 18F-FAPI PET/CT improves the specificity of lymph node diagnosis. Furthermore, compared to 68Ga-labeled tracers, 18F-labeled FAPI has better resolution potential due to its lower positron energy. Therefore, 18F-labeled FAPI holds significant clinical value and promising prospects.

4 Indications, Contraindications, and Precautions

4.1 Eligibility Criteria: Patients with suspected or confirmed lung cancer who have undergone 18F-FAPI PET/CT

4.2 Exclusion Criteria:

- (1) Concurrent presence of other active malignant tumors or a history of other malignant tumors within the past 5 years;
- (2) Severe uncontrollable diseases or active infections;
- (3) Ineligible participants for informed consent.

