7.2 Significance Level and Power of Clinical Studies

The significance level α was set at 0.05; the confidence level was 0.95.

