7.3 Statistical Methods

Statistical analysis was performed using SPSS 17.0. The diagnostic sensitivity, specificity, and negative/positive predictive values were calculated using a four-cell table. The area under the ROC curve and the optimal cutoff value (SUV optimal cutoff) were evaluated by ROC curve analysis. The consistency between 18F-FAPI PET/CT diagnosis and pathological diagnosis was assessed using the kappa test. A p-value <0.05 was defined as statistically significant.

Statistical analysis was performed using SPSS 17.0.

① Diagnostic performance evaluation, four-grid table index calculation:

Sensitivity = True positives / (True positives + False negatives) × 100%

Specificity = True Negative / (True Negative + False Positive) × 100%

Positive predictive value = true positive / (true positive + false positive)

Negative predictive value = true negative / (true negative + false negative)

② ROC curve analysis:

Calculate the area under the curve (AUC) and evaluate diagnostic performance (AUC>0.9 indicates excellent, 0.8-0.9 indicates good, 0.7-0.8 indicates moderate).

Determine the optimal cutoff for SUV using the maximum Youden index.

③ consistency check

The consistency between 18F-FAPI PET/CT and pathological diagnosis was evaluated using the Kappa coefficient.

Kappa>0.8: Excellent consistency;

0.6-0.8: High consistency;

<0.6: Consistency should be interpreted with caution.

Bilateral test, $p<0.05$ defined as significant difference.

④ survival analysis

Kaplan-Meier method:

Collect baseline PET parameters (lesion SUVmax, lesion SUVmean, MTV, LTV, bone marrow SUVmax, etc.), and plot PFS/OS curves according to treatment response (CR/PR vs. SD/PD), pathological response (e.g., MPR status), or PET parameter grouping (e.g., high/low SUVmax). Compare the significance of survival differences between groups using the Log-rank test ($p<0.05$).

Cox proportional hazards model:

Univariate analysis: Screening of clinical variables associated with PFS/OS (age, stage, SUVmax, MTV, etc.).

Multivariate analysis: Significant univariate variables ($p<0.1$) were included, with quantified hazard ratios (HR) and 95% confidence intervals.

Verify the proportional hazards assumption (Schoenfeld residual test).

8 Data Recording and Management

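### Overall survival by treatment response is timed from diagnosis although response is known only later, so the comparison is open to guarantee-time bias

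*Protocol*

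**What the plan says.** Protocol section 2.1.4 gives the only time origin in the document: "It tracks the time from diagnosis to specific events (e.g., CR, PR, SD, PD, recurrence, death"). The next sentence reads "Survival rates over time are plotted using Kaplan-Meier curves to visually compare survival differences across groups".

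Section 7.3 item ④ names the groups. PFS and OS curves are to be split by "treatment response (CR/PR vs. SD/PD), pathological response (e.g., MPR status"), or by PET parameters, which are to be taken at baseline ("Collect baseline PET parameters"). The test is the ordinary one: "Compare the significance of survival differences between groups using the Log-rank test", at p<0.05, in line with section 7.2 ("The significance level α was set at 0.05").

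The protocol does not fix when response is assessed. It does not say how a patient who dies before assessment, or who is never resected, is classified. It mentions no landmark, no restart of the clock and no time-dependent covariate.

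**The concern.** A log-rank comparison from a given origin is valid when group membership is known at that origin. Response is not known at diagnosis. Section 2.1.4 itself lists CR and PR among the events timed from diagnosis, and section 7.3 then treats them as fixed groups on that same clock.

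A patient must live to an assessment to be called CR or PR. Responders therefore carry a stretch of time in which they could not have died. If patients who die in that stretch are counted on the other side, the responder curve is better by construction. The log-rank test can then reject although response has no bearing on survival, and part of secondary endpoint ③ (prognosis) would rest on the time axis alone.

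**Working it through.** The protocol states no hazard ratio, event count or power for the survival analysis, so there is no figure of its own to reproduce. The check asks how far a null comparison moves under each reading that the text allows.

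**Inputs from the protocol.** Origin at diagnosis (2.1.4); groups CR/PR against SD/PD with an ordinary log-rank test (7.3 ④); α 0.05 (7.2); recruitment 36 months (section 9); 120 patients in total (7.1).

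**Assumptions, none of them in the protocol.** 100 patients in the OS comparison; 40% responding; exponential survival with median OS 12, 18 or 24 months; uniform accrual over 36 months and 12 months of further follow-up; first assessment at month 3; response unrelated to survival. Each setting was simulated repeatedly and tested with a two-sided log-rank test at 0.05.

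**Step 1: how many deaths are at issue.** The share dying before month 3 is 1 − 2^(−3/median):
- median 12: 1 − 2^(−3/12) = 15.9%
- median 18: 1 − 2^(−3/18) = 10.9%
- median 24: 1 − 2^(−3/24) = 8.3%

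Of 100 patients, about 16, 11 or 8 die before anyone can be CR/PR.

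**Step 2: effect on a null comparison of OS by response.**

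| Handling of deaths before assessment | Apparent HR | False-positive rate (nominal 5%) |
|---|---|---|
| Counted as non-responders, assessment at month 3 | 0.73 / 0.77 / 0.80 for median 12 / 18 / 24 | 27% / 17% / 11% |
| Dropped if before month 3, but response may be reached at month 3, 6 or 9 | 0.82–0.84 | 8–12% |
| Dropped, one fixed assessment | about 1.0 | about 5% |

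The second row stays biased because a patient who dies between months 3 and 9 is kept but has had fewer chances to be called a responder.

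**Step 3: sensitivity to timing.** A separate simulation used 120 patients, 40% responding, censoring uniform over 12 to 36 months, and early deaths counted as non-responders:
- assessment around month 3: HR 0.69 with 35% false positives (median 12), HR 0.77 with 14% (median 24)
- assessment around month 6: HR 0.52 with 78% (median 12), HR 0.58 with 45% (median 24)
- early deaths excluded, one assessment per patient: HR 0.98–1.01 with 4–6%

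Under the step 2 assumptions, an earlier assessment at month 2 gives 14% (median 12) and 9% (median 24). The later the assessment and the shorter the survival, the larger the bias.

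**Step 4: the remedy.** In that separate simulation, starting the clock at a landmark and keeping only patients still in follow-up gives HR 0.97–1.02 and 4–6% false positives in every setting.

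**Step 5: MPR.** MPR status is read from a resected specimen. Among resected patients, both groups share the same event-free run from diagnosis to surgery, so the contrast between them is near-unbiased. What remains is that curves drawn from diagnosis begin with time in which nobody in the set could fail.

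**The case against.** The best reply is that the inflated rates depend on a rule that the protocol never states. Read literally, a patient who dies unassessed is none of CR, PR, SD or PD, and falls in neither group. With one assessment per patient, that restores the nominal error rate. This stands, and it is why the highest figures are conditional. It does not clear the analysis. The protocol does not state the exclusion, and it fixes no assessment date, so response reached at later visits leaves 8–12% false positives even after exclusion.

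A reader might infer the same inflation for PFS and OS by MPR. The documents do not support that: it needs unresected patients to be labelled non-MPR, and nothing says so. A reader might also infer that nobody with an early progression can be in the favourable MPR group. That is firm for deaths but not for progressions, since a patient who progresses and is still resected could show MPR. Nor does section 7.3 name response as a Cox covariate; its list is age, stage, SUVmax, MTV and an open end.

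It can also be said that landmarks belong in a statistical analysis plan, which may exist. That would answer a plain omission. Here the protocol states an origin, groups and a test that do not fit together.

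**Conclusion.** The concern holds for OS by treatment response. With time counted from diagnosis, groups formed later and a plain log-rank test, the comparison is open to guarantee-time bias. Under the step 2 assumptions with a first assessment at month 3, the null false-positive rate runs from about 5% to about 27%, depending on how early deaths are handled and whether response can be reached at several visits; a later assessment makes it worse. All sizes rest on assumed survival, response rate, timing and numbers, so they illustrate the risk and do not predict it.

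For MPR the finding is limited to the choice of origin for the curves. PFS by response is left out because it has a separate problem: PD is both a group label and a PFS event. The baseline PET-parameter grouping and the primary diagnostic endpoint are untouched. The change should be made, but it concerns a secondary endpoint and does not threaten the trial's main result.

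**What to change.** In section 7.3 item ④:

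- Analyse OS by response from one fixed landmark assessment date. Include only patients alive and in follow-up at that date, and classify them by response up to it.
- Analyse PFS and OS by MPR from the date of resection, among resected patients only.
- If response is ever entered in the Cox model, make it a time-dependent covariate.
- State the origin for the baseline PET-parameter groups separately.

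This changes analysis wording only. It needs no added patients or visits, and the dates should already be in the records. The cost is that a few early events leave these secondary comparisons, and the results then apply to patients who reached the landmark or surgery.

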5.4 Study Endpoints

Primary endpoint: Diagnostic efficacy of 18F-FAPI PET/CT in lung cancer patients (sensitivity, specificity, accuracy)

secondary end points:

- ① Compare the diagnostic performance differences of 18F-FAPI PET/CT with CT, MR, and 18F-FDG PET imaging in clinical applications for lung cancer;
- ② Analysis of diagnostic differences in the subgroup of patients (pathological, genetic, etc.) using 18F-FAPI PET/CT;
- ③ Evaluation of 18F-FAPI PET/CT in predicting lung cancer prognosis.

6 Research Procedures and Operational Standards

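### Selecting Cox covariates by univariate p<0.1 can drop age and stage by chance and, separately, lets overlapping PET parameters weaken each other's adjusted hazard ratio

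*Protocol*

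**What the plan says.** Evaluating FAPI PET/CT for prognosis is the third secondary endpoint (Protocol 5.4: "Evaluation of 18F-FAPI PET/CT in predicting lung cancer prognosis"). Section 7.3, under survival analysis, sets the Cox procedure in two steps. The candidates are screened singly: "Univariate analysis: Screening of clinical variables associated with PFS/OS (age, stage, SUVmax, MTV, etc". The model is then filled from that screen: "Multivariate analysis: Significant univariate variables ($p<0.1$) were included, with quantified hazard ratios (HR) and 95% confidence intervals". No variable is kept regardless of its p-value, no PET parameter is named as the lead, and nothing is said about parameters that overlap.

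The candidate list is open-ended. The Cox item itself names SUVmax and MTV. A longer list stands just above it, under Kaplan-Meier: "Collect baseline PET parameters (lesion SUVmax, lesion SUVmean, MTV, LTV, bone marrow SUVmax, etc".

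Section 2.1.4 describes what the model is for: "Cox proportional hazards model multivariate regression quantifies the contribution of factors such as age and pathological stage to survival risk". Section 7.2 sets the error level ("The significance level α was set at 0.05; the confidence level was 0.95"). The protocol gives no event count, hazard ratio, correlation or power for the survival analysis.

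**The concern.** There are two problems, with different causes.

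**Age and stage.** Under 7.3 they enter the model only if each reaches p<0.1 alone. Section 2.1.4 expects the same model to quantify them. In a study of 120 patients, some only suspected of lung cancer, a real effect can easily miss that threshold. If stage drops out, the PET hazard ratio is unadjusted for stage, and the study cannot say whether FAPI adds prognostic information beyond stage.

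**Overlapping PET parameters.** SUVmax, SUVmean, MTV and LTV describe the same lesions. If one is prognostic, correlated companions tend to pass the screen with it. In the joint model they share the effect and inflate each other's standard errors, so a real PET effect may be reported as not independent. The reported confidence intervals also take no account of the selection.

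**Working it through.** The protocol has no survival power or event figure to reproduce; its only size calculation concerns diagnostic sensitivity.

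**Inputs from the protocol:** screen at p<0.1; alpha 0.05, taken as two-sided (7.3 states this under the kappa item); SUVmax and MTV named for the Cox screen, others possible.

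**Assumed inputs:** events D = 40 to 61; age HR 1.2 per SD; stage split 50:50 with HR 1.5 or 2; SUVmax HR 1.5 per SD; equal pairwise correlation r between PET parameters.

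**Step 1: chance of failing the screen.** P(fail) = 1 − Φ(√(D·v)·ln HR − 1.645), where v is the covariate's variance (1 per SD; 0.25 for a 50:50 split).

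- Age, D = 51: √51 × ln 1.2 = 7.141 × 0.1823 = 1.302; Φ(−0.343) = 0.37; fails in 63%. At 40 and 60 events: 69% and 59%.
- Stage, HR 2, D = 51: √12.75 × ln 2 = 3.571 × 0.6931 = 2.475; Φ(0.830) = 0.80; fails in 20%. At 40 and 60 events: 29% and 15%. With HR 1.5: 64% and 53%.

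A simulation of the full rule (100 cancers, about 51 events, SUVmax HR 1.5 per SD, 50:50 stage HR 2) gives 61-69% for age and 27-30% for stage. Stage fails more often than the formula suggests because a univariate fit that omits the other prognostic factors pulls the stage coefficient towards zero.

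**Step 2: cost of overlap, by formula.** Power = Φ(√(D(1−R²))·|ln HR| − 1.96) and VIF = 1/(1−R²). Take an effect with 80% power on its own, so √D·|ln HR| = 1.96 + 0.842 = 2.802. With two PET parameters R² = r²; with four equally correlated ones R² = 3r²/(1+2r). All are taken to enter the model.

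| PET parameters | r | VIF | Power |
|---|---|---|---|
| 2 | 0.5 | 1.33 | Φ(2.802×0.866−1.96) = 68% |
| 2 | 0.7 | 1.96 | Φ(2.802×0.714−1.96) = 52% |
| 2 | 0.8 | 2.78 | Φ(2.802×0.600−1.96) = 39% |
| 2 | 0.9 | 5.26 | Φ(2.802×0.436−1.96) = 23% |
| 4 | 0.7 | 2.58 | Φ(2.802×0.622−1.96) = 41% |
| 4 | 0.8 | 3.82 | Φ(2.802×0.511−1.96) = 30% |

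**Step 3: the rule simulated.** Here companions enter only if they pass the screen. The comparator is a fixed model of age, stage and SUVmax. Both columns give power for SUVmax.

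| Setting | Screened | Fixed |
|---|---|---|
| 2 parameters, r = 0.5, about 51 events | 70% | 80% |
| 2 parameters, r = 0.8, about 51 events | 38% | 81% |
| 4 parameters, r = 0.6 / 0.8 / 0.9, about 51 events | 45% / 24% / 14% | 74-82% |
| 4 parameters, r = 0.7, about 61 events (stage HR 1.8, age HR 1.15 per SD) | 40% | 82-86% |

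Power is roughly halved or worse from r of about 0.8 with two parameters and about 0.7 with four.

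**Step 4: error cost of the alternative.** With no PET effect, testing four PET parameters in four separate adjusted models gives at least one significant result in about 14-16% of trials, against 5-8% under the plan's rule. Separate models therefore need one designated lead.

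**The case against.** - **Size.** A reader might infer that the prognostic result loses most of its power. The documents do not support that. They give no correlation, and at r = 0.5 with two parameters the loss is only from 80% to 70%.
- **Reach.** Endpoint three is also served by log-rank tests, univariate Cox fits and the AUC comparison in 2.1.4. The screen affects none of these, only the adjusted HR. This stands.
- **Cause.** It is tempting to blame the power loss on losing age and stage. It comes from the overlap; losing age and stage is a matter of adjustment and of an undelivered aim.
- **Number of PET parameters.** The Cox item names two. The others are listed under Kaplan-Meier and reach the screen only through the open-ended wording, so four is a possibility, not a plan.
- **Conflict with 2.1.4.** Age and stage are given there as examples, and 7.3 does list both as candidates. It is a gap between aim and method rather than a flat contradiction, but the rule can still remove them.
- **Events.** Section 9 follows patients to death, so events may exceed 51. With two parameters, r = 0.6 and about 74 events, power is 79% against 93%: smaller, but still a loss.
- **Comparison.** It favours the fixed model, because the parameter fixed there is the truly prognostic one. This stands.
- **Deferral to a SAP.** A lead parameter and collinearity handling are often left to a SAP, which is not at hand. The p<0.1 rule is not left open, and a SAP that follows the protocol inherits it.

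**Conclusion.** The point holds in two separate parts. That the rule can remove age and stage follows from the text alone. Its frequency rests on assumptions: with about 51 events, about 61-69% of trials for age at HR 1.2 per SD and about 27-30% for a 50:50 stage covariate at HR 2. That overlapping PET parameters can enter together also follows from the text. More than half the power for an individual adjusted HR is lost only under strong correlation, about 0.8 with two parameters or 0.7 with four.

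No stated power figure is contradicted, and the unadjusted analyses are untouched. This concerns one analysis of a secondary endpoint. It is worth correcting because the rule is written down and the change is cheap.

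**What to change.** Replace the p<0.1 screen in 7.3 with a prespecified Cox model containing age, stage and one lead PET parameter (for example SUVmax). Make it the single tested model for each of PFS and OS, with age and stage kept whatever their p-values. Fit the other PET parameters one at a time with age and stage, labelled exploratory. Keep the univariate results as description only. Settle the lead parameter before outcomes are analysed.

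The cost is analysis wording, with the same patients and data. The downsides are several small models instead of one table, exploratory models that carry no error control, and the risk that the chosen lead is not the most prognostic parameter.

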8.1 Investigator Data Records

- 1) For all eligible participants who have signed the informed consent form, their relevant data and laboratory test results must be meticulously and thoroughly documented.
- 2) All imaging data were interpreted by two attending physicians with over 5 years of experience in nuclear medicine, and the chief physician provided the final consensus interpretation for any questionable cases.
- 3) Original data records, signed by the investigator and dated.

4) Confirm that all adverse events have been documented, and that serious adverse events have been reported and recorded in accordance with relevant procedures in a timely manner.

9 Expected Research Progress

Study recruitment period: 36 months

Observational study duration: This study was an observational study, with patient mortality serving as the endpoint of follow-up.

10 Adverse Event Assessment and Reporting

10.1 Definition of Adverse Events

Adverse medical events (AMEs) in clinical trials during follow-up, including discomfort symptoms, signs or abnormal laboratory findings, and imaging abnormalities.

10.2 Major Adverse Events

New-onset clinical symptoms (e.g., fever), laboratory abnormalities (e.g., liver enzyme levels exceeding 3 times the upper limit), exacerbation of pre-existing conditions (e.g., worsening cardiac function classification), or imaging abnormalities (e.g., pneumothorax).

10.3 Documentation of General Adverse Events

All directly observed and subject-reported adverse events should be documented on the electronic case report form.

Researchers should avoid colloquial expressions and use standardized medical terminology to record adverse events, which should at least include:

- ◆ Start and end dates
- ◆ order of severity
- ◆ causality
- ◆ Measures taken
- ◆ Outcome of Adverse Events

10.4 Recording and Reporting of Serious Adverse Events

During the study period, all serious adverse events shall be immediately reported by the investigator to the attending physician or nurse-in-charge, and simultaneously submitted in writing to the clinical research management department of the affiliated clinical research institution, with written notification to the study sponsor. The clinical trial management department shall submit a written report to the relevant ethics committee and the provincial, autonomous region, or municipal food and drug administration and health and family planning authorities where the clinical research institution is located within 24 hours. For death events, the clinical research institution shall provide the ethics committee and the study sponsor with all required documentation. Contact information is as follows:

Contact	contacts	contact number	portraiture
The First Affiliated Hospital of Zhejiang University School of Medicine	[name]	[name]	[name]

